Healthy Minds Program (HMP) App Dosage Study

Basic Study Information

[name]

NCT05229406

Minimal Risk Research Institutional Review Board

IRB Approval Date: 10/19/2022

[compiled from the non-protocol based IRB application]

Healthy Minds Program App Dosage Study

Principal Investigator: [name]

Funding: Mindfulness training delivered via mobile health to reduce depression and anxiety

1K23AT010879-01

Overall Purpose

This study will investigate the impact of dosage of meditation practice delivered via a mobile health smartphone application (Healthy Minds Program app) on symptoms of depression and anxiety. We will also investigate the feasibility and acceptability of this program among individuals with elevated symptoms of depression and/or anxiety at baseline.

Study Procedures and Interventions

We anticipate enrolling 110 participants into the study. Recruitment will take place via email, newspaper advertisements, Craigslist, clinics, and flyers. Interested individuals will complete a webscreen to determine eligibility. After passing the webscreen, they will be provided with an overview of the study and will have the option to enroll via an online consent process.

Participants will be asked to complete T1 surveys. After completing T1 surveys, they will be contacted by study staff and assigned to a dosage condition (low dosage = 5 minutes per day, high dosage = 15 minutes per day). Study staff will assist with downloading the mobile app, briefly introducing the participant to the meditation practices, and answering any questions about the practices and/or study. Participants will complete EMA assessments (brief questionnaires delivered as text messages to participants' mobile phones) throughout the duration of the study. Four EMA questionnaires will be delivered per day at random times interspersed between the hours of 9am and 7pm. Participants will complete T2 surveys approximately 4 weeks

after T1. Participants may be invited to an exit interview after completion of the study in order to give feedback on the study.

- Attitudes Towards Psychological Online Interventions (T1, T2)
- AUDIT C (screening only)
- Big Five Inventory, Conscientiousness Items (T1 only)
- Demographics (T1 only)
- Digital Working Alliance Inventory (T2 only)
- EMA items (daily throughout study)
- Experiences Questionnaire decentering subscale (T1, T2)
- Five Facet Mindfulness Questionnaire awareness subscale (T1, T2)
- Healthy Minds Index (T1, T2)
- Marlowe Crowne Social Desirability Scale (T1 only)
- Meaning in Life Questionnaire presence subscale (T1, T2)
- Medication and Therapy Questionnaire (T1, T2)
- Meditation Related Adverse Effects (T2 only)
- Mindfulness Adherence Questionnaire (T2 only)
- NIH Toolbox Loneliness (T1, T2)
- Perseverative Thinking Questionnaire (T1, T2)
- Pre/Post Practice Items (daily throughout study)
- PROMIS Anxiety and Depression Scales (screening, T1, T2)
- PROMIS Sleep Disturbance Scale (T1, T2)
- System Usability Scale (T2 only)
- Well-Being Growth Mindset (T1, T2)
- Qualitative interview questions (T2 only)
- How heard about the study (screening only)

HMP app: After randomization, participants will be asked to spend either 5 minutes or 15 minutes per day practicing meditation with guidance through the HMP smartphone app. The HMP app was developed by Healthy Minds Innovations at the UW Center for Healthy Minds, and is based on the work of [name]. It is designed to

promote psychological well-being through well-being skills training. HMP provides content with instruction administered through a curriculum of high-quality guided practices. HMP is based on research on eudaimonic well-being (e.g., environmental mastery, purpose) and brain-based skills that underlie these qualities (e.g., regulation of attention, mental flexibility). Participants will be instructed to use practices from the Awareness module of the HMP app. These attention skills are associated with a number of positive outcomes, including better physical and mental health and increased school and job success. Importantly, evidence increasingly suggests that these attention and awareness skills, specifically, can improve with meditation training. Within the context of the current study, the HMP app is being considered a general wellness device rather than a medical treatment.

Usage data: We will collect information on when and for how long participants listen to recordings, which recordings, and for how long through the application itself. Usage data will be collected through the app itself as well as through EMA questions. Information on their device make, model, and operating system is also collected through the application for quality assurance purposes. All data collected through the application is stored on Amazon Web Services (AWS). All data is encrypted, both at rest (when it is in a database) and in transit (e.g., when it is moving between the application and AWS services). No identifying information, such as IP address, is stored by the application. Data collected through the application will only be identified by study ID numbers.

Potential Benefits to Society

This program offers an innovative public health approach to reducing the burden of depression and anxiety. By investigating the impact of dosage, we will understand the amount of practice that may be necessary to produce clinical benefits.

Inclusion Criteria

1. Elevated symptoms of depression and anxiety.
2. Age 18 or older.
3. Proficient in English.

Exclusion Criteria

1. Non-elevated symptoms of depression and anxiety or having a t-score greater than 70 on the depression scale.
2. Age 17 or younger.
3. Significant meditation experience (as defined below):
 - Meditation retreat experience (meditation retreat or yoga/body practice retreat with significant meditation component).
 - Regular meditation practice weekly for over 1 year OR daily practice within the previous 6 months.
 - Previous practice under the instruction of a meditation teacher, other than in the context of an introductory course.
4. Elevated scores on the Audit-C (greater than or equal to 4 for men and greater than or equal to 3 for women).
5. No access to a smartphone capable of running the HMP app.
6. Self-reported unwillingness to complete EMA surveys 4 times per day during the 4 week study.

Recruitment Plan

These are the primary tools we plan to use for recruitment:

- 1) Flyers: We intend to post in neighborhood settings (e.g., grocery stores, libraries, community centers). We may post at area clinics as well.
- 2) Email: We anticipate using DoIT to email members of the UW-Madison campus community. We may also email UW-Madison community contacts and Madison community contacts directly.
- 3) Newspaper: We anticipate posting advertisements for the study in local newspapers (e.g., The Isthmus).
- 4) Craigslist (under research heading).

Targeted versions of recruitment materials may be used to increase enrollment from underrepresented groups.

Sharing of Data

De-identified data will be made available upon request or shared publicly in an open science format, consistent with NIH data sharing guidelines.

Data that is shared upon request or shared publicly will be completely stripped of HIPAA identifiers including dates.

## **Analysis approach**

The feasibility and acceptability of the HMP app for individuals with depression and anxiety will be assessed using benchmarks previously recommended for mHealth research (Hermes et al., 2019). The app will be considered acceptable if ≥75% of participants complete the intervention and adhere to treatment for an average of 7- or 3-minutes per day (for the 15- and 5-minute dosage conditions), 6 days per week. A usability score > 70 on the Systems Usability Scale (Bangor et al., 2008) will be considered acceptable. As our study is not designed nor powered for definitive effectiveness analyses, Cohen's (1988) d effect sizes will be used to estimate the magnitude of pre-post changes in symptoms of depression and anxiety. The effect of group assignment on practice dosage will be analyzed using analysis of variance (ANOVA) covarying gender. The relationship between practice dosage and changes in depression and anxiety will be assessed using ordinary least squares regression (OLS) models predicting post-treatment symptom levels while controlling for pre-treatment symptoms and gender. Intensive longitudinal data (i.e., ecological momentary assessment data) will be analyzed using dynamic structural equation modeling (DSEM), accounting for the nesting of observations longitudinally within participants. Cross-lagged models will be constructed to evaluate the temporal sequencing between practice time with mood symptoms (depression, anxiety) and candidate mechanisms (decentering, repetitive negative thinking). DSEM will allow both practice dosage and outcomes (symptoms, mechanisms) to be modeled simultaneously (Hamaker et al., 2018). DSEM also allows assessment of between-person variability in cross-lagged relationships that can inform power analysis for future studies as well as provide substantively useful information regarding individual differences in the link between practice dosage, symptoms, and mechanisms.

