## Power analysis

Power analyses are based on effect sizes from mindfulness-based interventions for individuals with depression and anxiety reflecting (1) pre-post changes in depression and anxiety and (2) association between practice dosage and changes in psychological symptoms. For pre-post changes in depression and anxiety, Goldberg et al. (2018) conducted a meta-analysis of mindfulness-based interventions (MBIs) versus no treatment control conditions in individuals with depression or anxiety and found mean between-group effects in the moderate to large range (ds = 0.59 and 0.89, for depression and anxiety, respectively). To our knowledge, no meta-analysis has been conducted evaluating pre-post changes in depression and anxiety within clinical samples using mobile health MBIs. Moderate to large reductions in depression symptoms have been reported in several mobile health MBI studies with depressed samples (d = 1.09 in Dimidjian et al., 2014, ds = 1.15 to 1.21 in Ly et al., 2014) and large reductions in anxiety have also been reported in anxious samples (d = 1.33; Boettcher et al., 2014).

For the association between practice dosage and changes in psychological symptoms, Parsons et al. (2017) conducted a meta-analysis showing a small magnitude correlation (r = .26). Data from a pilot study using the HMP app in a very small sample (n = 10) also showed moderate-to-large reductions in *DASS-21* stress (d = 0.78) and a correlation between practice time and pre-post changes in stress (r = .27); however, small studies provide a poor basis for conducting power analysis (Leon et al., 2011).

Power for between-group differences in dosage based on randomization to dosage conditions can be roughly estimated based on our preliminary feasibility data (n = 85). Participants will be randomized to 15- and 5-minute dosages. Our naturalistic pilot data showed a mean practice time of 3.91 minutes per day (SD = 3.15, range = 0.0 to 12.2). Assuming randomization produces a 3-minute mean difference between groups (e.g., means of 7 and 4 minutes per day, for 15- and 5-minute dosage conditions) and doubles the standard deviation, there would be a between-group effect of d = 0.48.

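### The only comparison of assigned arms (practice dosage) adjusts for gender alone; prespecifying two T1 measures already collected would be a nearly free, modest gain in precision of unknown size

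*SAP*

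**What the plan says.** SAP, Analysis approach: practice dosage is compared between the assigned groups by "analysis of variance (ANOVA) covarying gender". No other covariate is named for this comparison. In the SAP text available, it is the only analysis that compares the arms as assigned. Symptoms are handled by pre-post effect sizes, by regression on practice dosage and by dynamic structural equation models.

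SAP, Power analysis, gives the planning assumption: "Assuming randomization produces a 3-minute mean difference between groups (e.g., means of 7 and 4 minutes per day", for the 15- and 5-minute conditions, and the pilot SD of 3.15 is doubled, so that "there would be a between-group effect of d = 0.48". The same section plans 90 participants, expects 81 with complete T1-T2 data, and states 85% power for this comparison.

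Protocol, Study Procedures and Interventions, lists "Big Five Inventory, Conscientiousness Items (T1 only" and "Attitudes Towards Psychological Online Interventions (T1, T2" among the measures. T1 surveys are completed before the dosage condition is assigned. The same section anticipates 110 participants. Under Usage data, practice time comes from the app itself and from EMA questions.

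**The concern.** The SAP already accepts covariate adjustment for this comparison, so the only question is which covariates to use. A baseline measure that predicts app use removes its share of practice-time variance from the error term and narrows the interval for the arm difference. Conscientiousness and attitude to online interventions are plausible candidates. They are measured before assignment, so adjusting for them cannot bias the randomised contrast.

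Precision matters here because the plan assumes a large spread around a 3-minute difference. The SAP also wants the study to supply effect sizes for planning later trials, and a narrower interval serves that aim whether or not a test is significant. This is a point about the precision of the arm comparison. It is separate from confounding in the regression of symptoms on practice dosage.

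**Working it through.** **Inputs.** From the SAP, Power analysis: mean difference 3 min/day; SD 2 × 3.15 = 6.30; N = 90 planned and 81 complete. From the protocol: N = 110. Assumed because not stated: two-sided 5% and 1:1 allocation. Two-sided 5% is reasonable, since the SAP's 80% power for a pre-post d of 0.32 at n = 81 comes out at 81% with it. Also assumed: R², the share of within-arm practice-time variance that the two T1 scores explain beyond gender. The documents give no value, so 0, 0.05, 0.10 and 0.20 are shown.

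**Effect size.** 3 / 6.30 = 0.476, which the SAP gives as 0.48. This reproduces.

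**The plan's stated power.** The SAP states 85% at this effect size. A two-sample t-test at d = 0.48 gives 56.9% at N = 81, 61.5% at N = 90 and 70.4% at N = 110. Using 81 per arm gives 85.9%, but that is not the planned design. The 85% does not reproduce at any stated total.

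**Formula.** Power = P(|T| > t(0.975, df)), where T is noncentral t with

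λ = [d / √(1 − R²)] × √(n₁n₂ / N).

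df = N − 3 for arm and gender, and N − 5 with the two T1 scores added. Gender is taken to leave the planning SD unchanged.

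Example at N = 81 (40 and 41):
- Gender only: λ = 0.48 × √(40 × 41 / 81) = 2.160, power 56.9%.
- R² = 0.10: 0.48 / √0.90 = 0.506, λ = 2.277, power 61.3%.

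| N | Gender only | + T1, R² = 0 | + T1, R² = 0.05 | + T1, R² = 0.10 | + T1, R² = 0.20 |
|---|---|---|---|---|---|
| 81 | 56.9% | 56.9% | 59.0% | 61.3% | 66.4% |
| 90 | 61.5% | 61.5% | 63.7% | 66.0% | 71.1% |
| 110 | 70.4% | 70.3% | 72.5% | 74.8% | 79.6% |

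Before rounding, the loss at R² = 0 is under 0.1 point in every row.

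**Interval width.** The ratio is √(1 − R²): 0.975, 0.949 and 0.894, so 2.5%, 5% and 11% narrower. At N = 81 the gender-only 95% interval is 2 × 1.991 × 6.30 × √(1/40 + 1/41) = 5.6 minutes wide. At R² = 0.10 it is 5.3 minutes.

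**Equivalent sample size.** 1 / (1 − R²) gives about 5%, 11% and 25% more participants.

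**R² needed for 80% power.** About 0.42 at N = 81, 0.35 at N = 90 and 0.21 at N = 110.

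**The case against.** The strongest reply is that nothing here is wrong. A randomised comparison with one prespecified covariate is valid and unbiased, and almost any trial with baseline data could attract this comment. That stands, and it is why the point is only an optional improvement.

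A reader might infer that the plan ignores known predictors of engagement. The documents do not support this. The protocol only lists the instruments, and neither document reports their correlation with practice time or describes them as predictors of app use. The gain may be zero.

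A reader might also take 57% as the power of this comparison. It belongs to the 81 participants with complete T1-T2 data. Practice time is logged by the app and need not depend on T2 completion, so 90 may be analysable, or more if the protocol's 110 applies. All these figures also rest on the doubled SD, which the SAP presents as a rough assumption. For the same 3 minutes at N = 81, power would be 99% at the pilot SD of 3.15 and 81% at 1.5 times it.

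The formula assumes equal variances and a common covariate slope in both arms. A mean of 4 with an SD near 6.3, on an outcome that cannot be negative, implies skew, so the power figures are approximate.

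Finally, the 85% power statement is the larger error. That is correct, but it is a separate one, and correcting it does not remove the case for using baseline data already collected.

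**Conclusion.** The point holds as a minor one. The only arm comparison in the available SAP text adjusts for gender alone, while two plausible pre-assignment covariates are already collected. Adding them costs under 0.1 point of power if they explain nothing. It gains about 2, 4 or 9 to 10 points if they explain 5%, 10% or 20% of practice-time variance. Those shares are assumptions, so the true gain cannot be computed from the documents.

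It would be tempting to conclude that adjustment repairs the power of this comparison. The figures do not support that. At N = 81 the two scores would need to explain about 42% of the variance to reach 80%, twice the top of the range considered. Only at N = 110 with R² near 0.20 does power come close.

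**What to change.** In the SAP, Analysis approach, prespecify an ANCOVA of practice dosage on assigned arm with gender, T1 conscientiousness and T1 attitudes towards online interventions as covariates. Use T1 values only: attitudes are measured again at T2, and that value could be affected by the assigned arm. Analyse all randomised participants with app usage data, whether or not they completed T2, and report the gender-only result alongside. Naming the covariates before the data are seen also rules out choosing them later by their results.

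The cost is one line in the SAP and two degrees of freedom, with no new data. Separately, correct the 85% power statement, state alpha and the allocation ratio, and reconcile the planned sample sizes of 90 and 110.

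### The practice–symptom regression uses achieved practice and adjusts only for pre-treatment symptoms and gender, leaving out three relevant T1 scales, so its slope can be confounded to an unknown extent.

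*SAP*

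**What the plan says.** Under Analysis approach, the SAP states: "The relationship between practice dosage and changes in depression and anxiety will be assessed using ordinary least squares regression (OLS) models". The covariate set is short, since the SAP describes the regressions as "predicting post-treatment symptom levels while controlling for pre-treatment symptoms and gender". Practice dosage here means achieved practice. The preceding sentence of the SAP makes it the outcome of an ANOVA on group assignment, so it is distinct from the arm itself.

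The measure list in the protocol (Study Procedures and Interventions) includes three baseline scales that bear on adherence and self-report:

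- "Attitudes Towards Psychological Online Interventions (T1, T2"
- "Big Five Inventory, Conscientiousness Items (T1 only"
- "Marlowe Crowne Social Desirability Scale (T1 only"

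On timing, the same section says: "After completing T1 surveys, they will be contacted by study staff and assigned to a dosage condition". All three T1 scores therefore precede assignment. On awareness of dose, the HMP app paragraph says that "participants will be asked to spend either 5 minutes or 15 minutes per day practicing meditation". The symptom measures are questionnaires: "PROMIS Anxiety and Depression Scales (screening, T1, T2". The Usage data paragraph says that practice is recorded by the app and also asked about in EMA questions. The SAP does not say which source enters this model.

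The SAP sections available (Analysis approach and Power analysis) give the three scales no role. The part of the SAP before Analysis approach was removed and could not be checked.

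**The concern.** Randomisation protects a comparison of arms. It does not protect a regression on how much each person chose to practise. Someone well disposed to online interventions, or conscientious, may practise more and also report more improvement for reasons other than the practice. Someone inclined to give favourable answers may report more improvement and, if practice is taken from EMA answers, more practice too. Adjustment for T1 symptoms and gender leaves these routes at least partly open.

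The SAP closes by saying that the study can supply effect sizes for planning later work. A practice slope that partly reflects who adheres would mislead that planning. If the shared influences run in the same direction, a later study sized on the slope would be too small.

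**Working it through.** **1. The plan's own figure.** Power analysis gives 67% power for r = .26 with 81 completers (90 less 10%). A noncentral F test of one slope, with noncentrality n·r²/(1 − r²), n = 81 and two-sided alpha .05 (assumed; none is stated), gives 66.8%. The figure reproduces.

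**2. How much of practice is set by assignment.** Power analysis assumes a 3-minute difference between arms and doubles the pilot SD of 3.15:

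- d = 3/(2 × 3.15) = 0.48
- With arms of equal size (assumed), r = d/√(d² + 4) = 0.48/√(0.2304 + 4) = .23
- r² = .054, about 5%

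On the plan's own assumption, about 95% of the variance in practice is not determined by the arm.

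**3. Size of the possible bias.** No document gives a correlation for any of these scales, so the inputs are assumptions. After T1 symptoms and gender, let each acting scale correlate a with practice and b with residual improvement, with the same sign, and let practice itself have no effect. For m scales with a common intercorrelation ρ, the spurious correlation is

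s = m·a·b / (1 + (m − 1)ρ).

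If b = 0, then s = 0. Otherwise, with a = b:

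| Case | a = b = .15 | a = b = .25 |
|---|---|---|
| One scale acts | .15² = .02 | .25² = .06 |
| Three scales, ρ = .3 | 3 × .15²/1.6 = .04 | 3 × .25²/1.6 = .12 |
| Three scales, ρ = 0 | 3 × .15² = .07 | 3 × .25² = .19 |

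As a share of the planning value .26 (from unrounded values), these are 9% to 24%, 16% to 45%, and 26% to 72%.

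**4. Consequence for the test.** With n = 81, the standard error on the Fisher z scale is 1/√78 = .11. With no true practice effect, the nominal 5% test would be significant about 5% to 9% of the time if one scale acts, 7% to 18% with three overlapping scales, and 9% to 39% with three uncorrelated scales.

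**5. Consequence for an observed .26.** The adjusted partial correlation is (.26 − s)/(1 − s) when a = b. It would be .24 to .21 (one scale), .23 to .16 (three, ρ = .3) or .21 to .09 (three, ρ = 0). To account for the whole of .26, a single composite would need a = b = √.26 = .51. The largest case in the table corresponds to √.1875 = .43.

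**6. Cost of adjusting.** Going from two to five covariates, power for a partial r of .26 moves from 66.8% to 66.7% (noncentral F) or from 64.1% to 62.3% (Fisher z).

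**The case against.** The strongest reply has five parts.

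- **Modest claims.** The SAP calls this a relationship, says that the study is neither designed nor powered for definitive effectiveness analysis, and does not expect definitive causal evidence. That stands, and the plan should not be read as claiming a causal slope. But the caveat concerns what random assignment can show. It does not mention confounding of achieved practice, and the same sentence offers effect sizes for planning.
- **Response style is partly handled.** A stable reporting habit affects T1 and T2 symptoms alike, and T1 symptoms are in the model. If practice comes from the app log, answering to please cannot raise it directly. Both points stand and weaken the case for the social desirability scale in particular.
- **Adjustment cannot repair the lack of blinding.** T1 scores precede knowledge of dose, the attitude scale is only a proxy for expectancy, and conscientiousness is neither expectancy nor response style. This stands too.
- **Adjustment is not always an improvement.** A covariate that predicts practice but hardly predicts outcome costs precision and can amplify residual confounding. This is a reason to report both coefficients rather than replace one with the other.
- **Other analyses exist.** The SAP plans dynamic structural equation models of practice and mood. If these separate within-person effects, stable traits do not confound those effects. That does not mend the regression slope.

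A reader might infer that the planned slope would be mainly expectancy and response style, or that a bias of a quarter to nearly three quarters of .26 has been shown. The documents support neither. The upper figures need all three scales to act at the assumed values in the same direction without overlap, and zero is not ruled out.

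**Conclusion.** The concern holds in a limited form. The practice–symptom slope rests on an exposure that is mostly not set by randomisation, and it is adjusted for two covariates only. Three relevant baseline scores, already collected before assignment, are unused in the SAP text available.

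The possible bias runs from zero, through about .02 to .06 in r if one scale acts, to about .04 to .19 if all three do. The non-zero figures rest entirely on assumed correlations of .15 to .25, same-sign effects, and scale intercorrelations between 0 and .3. Neither size nor direction can be derived from the documents. That participants know their dose is inferred from their being told the minutes; the documents do not discuss blinding.

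A reader might extend this to the ANOVA of assignment on practice. That comparison is randomised and is not affected.

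**What to change.** In Analysis approach, pre-specify a second regression for depression and for anxiety that adds the T1 scores for attitude to online interventions, conscientiousness and social desirability. Use the T1 attitude score only, because the T2 score may itself be changed by the app. Report its practice coefficient and confidence interval beside those of the planned model.

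State that either slope is an association. If the two coefficients differ, carry both forward as the range for planning later studies. Name the source of practice time (app log or EMA), since response style enters more readily through self-report. Say also that adjustment is partial and leaves expectancy that arises once participants know their dose.

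The cost is SAP wording, three degrees of freedom out of about 81 completers, and at most about 2 points of power for a given partial correlation. No new data are needed.

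### The DSEM leaves out randomised arm, so the slope variability it calls individual differences may contain an arm component of unknown size

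*SAP*

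**What the plan says.** The Protocol (Study Procedures and Interventions) defines two conditions, "low dosage = 5 minutes per day, high dosage = 15 minutes per day", and the SAP (Power analysis) confirms that "Participants will be randomized to 15- and 5-minute dosages".

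The SAP (Analysis approach) models the EMA series by DSEM, with observations nested in participants and cross-lagged paths linking practice time to mood symptoms and candidate mechanisms. It gives the between-person variability of those paths two uses. One is planning: "DSEM also allows assessment of between-person variability in cross-lagged relationships that can inform power analysis for future studies". The other is interpretation, as "substantively useful information regarding individual differences in the link between practice dosage, symptoms, and mechanisms". The Power analysis section adds that the heterogeneity of the day-to-day association is not known at present and that this study will supply it.

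Arm appears in one analysis only, the ANOVA of practice dosage. The DSEM text names no arm predictor, no arm-by-slope term and no multiple-group model. It does not say whether slopes will be reported raw (per minute) or standardised within person.

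**The concern.** The DSEM has a random slope for each person. If its mean differs between the arms and arm is not in the model, the arm difference becomes part of the person-to-person variance. That variance is the figure the SAP means to hand on. Any arm component would be labelled as individual differences, and a later single-dose trial would plan on a slope variance that is too large. The part of its sample size that scales with slope variance would be overstated in the same ratio.

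There are two plausible routes to an arm difference in mean slope:

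- **Shape of the dose-response.** If much of the within-person contrast is session versus no session, and sessions are longer in one arm, the per-minute slope is equal across arms only when benefit is proportional to minutes. The plan neither assumes nor justifies proportionality. The Protocol's stated aim of learning how much practice is needed leaves the shape open.
- **Scaling.** A slope standardised within person is multiplied by that person's practice SD. If day-to-day spread differs by arm, equal raw slopes become unequal standardised ones.

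In a dosage study, the arm difference in slopes is also a result of interest, and the visible plan would leave it unreported.

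**Working it through.** **The plan's own figure.** The only stated figure on how far the arms differ concerns the amount of practice. The SAP (Power analysis) assumes "means of 7 and 4 minutes per day, for 15- and 5-minute dosage conditions" and, from a pilot SD of 3.15, that randomisation "doubles the standard deviation, there would be a between-group effect of d = 0.48". Check: (7 − 4)/(2 × 3.15) = 3/6.30 = 0.476, which rounds to 0.48. It reproduces. The SAP gives no figure for slopes, slope variance or DSEM power.

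**Variance decomposition.** Let Δ be the arm gap in mean slope, τ the within-arm slope SD and p the fraction in one arm. Then

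pooled variance = τ² + p(1 − p)Δ², which is τ² + Δ²/4 at 1:1.

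The allocation ratio is not stated, so 1:1 is an assumption. For a given Δ it gives the largest arm component. The ratio of pooled to within-arm variance is 1 + (Δ/τ)²/4:

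| Δ/τ | 0 | 0.25 | 0.5 | 1 | 2 |
|---|---|---|---|---|---|
| Ratio | 1.00 | 1.02 | 1.06 | 1.25 | 2.00 |

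The documents give neither Δ nor τ.

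**Size under a dose-response curve.** Assume session lengths L of 5 and 15 minutes and benefit per session proportional to L^g. The per-minute slope is then proportional to L^(g−1). Let R be half the arm gap divided by the mean of the two slopes, and c the within-arm CV of the slope (assumed). Then

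arm share = R² / [R² + c²(1 + R²)].

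Worked case, g = 0: the slopes are 1/5 = 0.200 and 1/15 = 0.067, with mean 0.133 and half-gap 0.067, so R = 0.50. With c = 0.3 the share is 0.25/(0.25 + 0.09 × 1.25) = 0.25/0.3625 = 69%.

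| g | R | c = 0.3 | c = 0.5 | c = 1 |
|---|---|---|---|---|
| 0 | 0.50 | 69% | 44% | 17% |
| 0.5 | 0.27 | 43% | 21% | 6% |
| 0.75 | 0.14 | 17% | 7% | 2% |
| 1 | 0 | 0% | 0% | 0% |

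At c = 0.3 the ratio of pooled to within-arm variance, 1/(1 − share), is 3.2, 1.7, 1.2 and 1.0 down the column.

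**Smaller contrast.** Suppose actual lengths were 4 and 7 minutes, borrowing the SAP's daily means. At g = 0 the slopes are 0.250 and 0.143, so R = 0.0536/0.1964 = 0.27 and the share is 43% (c = 0.3) or 22% (c = 0.5). At g = 0.5, R = 0.14 and the share is 17% (c = 0.3).

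**Simulation check.** Assumptions: 90 people, 28 or 112 occasions, arm means of 4 and 7 minutes, mean slope −0.06 and within-arm slope SD 0.03 per minute. Same-time slopes stood in for lagged ones. Ratios of pooled to within-arm slope variance:

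- Same per-minute effect in both arms, raw slopes: 1.00, whether within-person practice SDs were 3 and 3 or 2 and 6.
- Arm gap of 1τ: 1.26 to 1.27. Arm gap of 2τ: 1.99 to 2.02.
- Logarithmic dose-response, no arm effect on the person's own parameter: 1.12 to 1.13.
- Linear effect, slopes standardised within person: 1.00 to 1.01 with equal practice SDs, 1.83 to 1.93 with SDs of 2 and 6.

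**Limit of an arm adjustment.** Take g = 0, no true individual differences, and session lengths that vary between people within an arm (lognormal, CV v). The inverse of a lognormal length has the same CV, so the within-arm part of the spurious variance is v²(1 + R²)/[R² + v²(1 + R²)]. With R = 0.50 this is 17%, 44% and 64% for v = 0.2, 0.4 and 0.6. Adjusting for arm removes only the rest.

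**The case against.** A reader might infer that assignment to 5 or 15 minutes creates slope variation by design, so that the reported variance is bound to be inflated. The documents do not support that. Assignment changes the amount of practice. It changes the slope of symptoms on practice only if the dose-response is not proportional, if the arms differ in effect per minute, or if slopes are standardised and practice variance is unequal. None of these is established, and with a proportional raw effect the ratio is 1.00.

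The other counter-arguments stand in part:

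- The 69% assumes that a 15-minute session helps no more than a 5-minute one, and the 30% CV is not in the documents. Both are illustrations.
- Session length is not fixed at 5 or 15. The SAP counts averages of 7 and 3 minutes a day as adherent for the longer and shorter conditions, and it expects daily means of 7 and 4. These are daily averages, so full sessions on fewer days are also possible. The contrast in actual length is open.
- Pooled variance is the right input for a future trial mixing the same two doses.
- The SAP sentence describes what DSEM permits and rules out no person-level predictor. Part of the SAP was unavailable, so the absence of arm is judged on Analysis approach and Power analysis. The study also presents itself as preliminary.

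These points limit the size and certainty of the problem. They do not remove it. On the visible text, pooled variability is given an individual-difference reading, and nothing planned would show whether arm contributes to it.

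**Conclusion.** The concern holds as a conditional one. The available SAP omits randomised arm from the DSEM while treating pooled variability in the cross-lagged slopes as individual differences and as an input to later power analysis. If mean slopes differ by arm, that variance includes Δ²/4 at 1:1 allocation.

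The size cannot be fixed from the documents. The arm share runs from 0%, for a proportional effect on the raw scale, through 17% and 43% to 69% for g = 0.75, 0.5 and 0, given assumed lengths of 5 and 15 minutes and a within-arm CV of 30%. It is smaller if actual lengths differ less or true heterogeneity is larger. The pooled figure would be too large only for a single-dose or arm-adjusted design. Even the within-arm variance is not a pure individual-difference figure when session length varies within arm.

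The change is worth making because the quantity is a stated product of the study and the adjustment costs almost nothing.

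**What to change.** In the DSEM section of the SAP:

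1. Regress the random cross-lagged slopes, and the person means, on assigned arm at the between-person level.
2. Report the arm difference in slopes with its interval, and both the pooled and the residual within-arm slope variance. Say which suits which future design: pooled for a trial mixing the same two doses, within-arm for a single-dose or arm-adjusted one.
3. State whether slopes are raw per minute or standardised within person.
4. Add a sensitivity run with practice coded any or none since the last prompt, because variable session length within an arm can also create apparent slope variation.

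Cost: one between-person covariate and one extra model run, with slightly longer estimation and no new data.
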